## LIST OF ABBREVIATIONS

Abbreviation or Term	Definition
CDC	Centers for Disease Control and Prevention
HIPAA	Health Insurance Portability and Accountability Act
HPV	Human Papillomavirus
MCHS	Marshfield Clinic Health System
MenACWY	Meningococcal Conjugate Vaccine
Tdap	Tetanus, Diphtheria, and Acellular Pertussis Vaccine

## I. PROTOCOL SYNOPSIS

Study Sponsor: Centers for Disease Control and Prevention (CDC)
Title: COVID-19 Booster Dose Reminder/Recall for Adolescents
Study Short Name: COVID-19 Booster Reminders
Study Rationale: Uptake of COVID-19 booster vaccines among adolescents in the United States is suboptimal. Booster dose coverage is significantly lower among adolescents aged 12-17 years relative to older age groups. Patient reminder/recall systems have been shown to be an effective strategy to increase vaccination among patients of all ages.
Study Objective: To assess the efficacy of a one-time reminder/recall for COVID-19 booster dose among eligible adolescents in a regional rural healthcare system.
Study Design: We will conduct a 1:1 randomized intervention by sending a one-time reminder/recall notice to parents of 12-17 year-olds due for a COVID-19 booster dose. Those randomized to the intervention arm will receive a one-time reminder/recall via their parent's preferred method of communication (mailed letter, text, email) while the usual care (control) arm will not receive any reminder/recall notice. This study will be conducted at a single integrated healthcare system serving patients in central, northern, and western Wisconsin.
Endpoint: The primary endpoint will be receipt of COVID-19 booster dose within 90 days of randomization.
Analysis: Analyses will compare receipt of COVID-19 booster dose among adolescents assigned to the intervention versus usual care.

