## II. BACKGROUND

To increase protection against SARS-CoV-2 infection, a single COVID-19 booster dose was recommended in the United States for adolescents aged 16-17 years in December 2021 and 12-15 years in January 2022. Uptake of the first COVID-19 booster dose among children and adolescents has been suboptimal. As of August 2022, booster dose coverage among adolescents aged 12 through 17 years was 33% compared to 70% among adults aged  $\geq 65$  years.

Centralized reminder and recall systems have been shown to be a cost-effective strategy to increase vaccination rates. Reminder and recall at Marshfield Clinic Health System (MCHS) are centralized and target young children aged 18-23 months and adolescents aged 12 years. In accordance with CDC and MCHS vaccination recommendations, COVID-19 vaccine was added to the reminder/recall letters for 12-year olds due for tetanus, diphtheria, and acellular pertussis vaccine (Tdap), meningococcal conjugate vaccine (MenACWY), or human papillomavirus (HPV) vaccine in the summer of 2021.

Beginning January 2022, individuals aged 12 and older who have completed the primary series were eligible to receive COVID-19 boosters. We propose to assess the efficacy of a one-time reminder/recall targeting adolescents aged 12-17 years who are eligible, but have not yet received the booster vaccine.

[figure not shown]
The intervention will leverage the existing MCHS's centralized reminder/recall system and process for enrolling patients for text and email communication regarding appointments and healthcare updates. The proposed intervention is a component of a larger project funded by the Centers for Disease Control and Prevention (CDC) to understand and address determinants of rural-urban differences in vaccine uptake among adolescents in the upper Midwest (NCT05148559).

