## **VI. INTERVENTION**

The intervention (reminder/recall) consisted of a one-time booster dose reminder sent to parents using their specified preferred communication method (postal mail, email, or text). The default preferred communication method will be postal mail (letter) if text or email is not specified in the electronic health record. The reminder/recall message will differ for those who will receive text versus letter or email, due to restrictions on privacy and length of text messages ([APPENDIX](#)). The usual care group will not receive the reminder/recall until after the 90-day evaluation period. All persons in the usual care group will receive the reminder/recall via mailed letter.

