### **A. Randomization**

Eligible adolescents will be stratified based on communication method and rurality (using home address). Each patient who is eligible at the time of data extraction/randomization will be assigned a random number, which will be used to facilitate stratified random sampling. Within each strata, the random number will be used to assign patients to intervention (reminder/recall sent via postal mail, text or email) or usual care (no reminder/recall) arm in a 1:1 ratio.

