### **A. Sample Size and Power**

This was a system-wide initiative with the intention that all eligible adolescent patients receive the reminder/recall. Therefore, power calculations were not done. We estimate about 18,600 MCHS adolescent patients aged 12-17 years, of whom, 25% or about 4,650 have completed the COVID-19 primary series and may be due for the booster dose.

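### Does the synopsis contradict the rest of the protocol by saying that controls get no reminder of any kind?

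*Protocol*

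**What the plan says.** The protocol describes the control condition in four places.

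- **Section I, Protocol Synopsis (Study Design):** the "usual care (control) arm will not receive any reminder/recall notice". The same synopsis sets the endpoint as booster receipt within 90 days of randomization.
- **Section VI, Intervention:** "The usual care group will not receive the reminder/recall until after the 90-day evaluation period". The next sentence adds: "All persons in the usual care group will receive the reminder/recall via mailed letter".
- **Section VI.A, Randomization:** the control arm is labelled "usual care (no reminder/recall) arm in a 1:1 ratio".
- **Section VIII.A, Sample Size and Power:** the project was run "with the intention that all eligible adolescent patients receive the reminder/recall". This is given as the reason for making no power calculation.

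Section II, Background, describes the existing reminder programme. Its reminders "are centralized and target young children aged 18-23 months and adolescents aged 12 years", and "COVID-19 vaccine was added to the reminder/recall letters for 12-year olds due for tetanus, diphtheria, and acellular pertussis vaccine" (or for the meningococcal or HPV vaccine) in summer 2021.

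**The concern.** Two things look wrong on a first reading.

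First, the synopsis describes controls who are never reminded, while Section VI describes controls who are reminded late. Those are different comparators. A report drafted from the synopsis alone would misdescribe the control arm.

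Second, the word "any" in the synopsis sits uneasily with the Background. Twelve-year-olds belong to the trial population, and some of them may receive routine letters that name COVID-19 vaccine. If the synopsis were applied literally, those letters would be held back from controls but not from the intervention arm. The difference between arms would then reflect more than the study reminder. The protocol does not say whether the routine letters run during the 90 days, whether both arms get them, or whether they mention the booster.

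At stake is whether the estimated difference can be read as the effect of the study reminder added to usual care.

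**Working it through.** **1. The plan's own figure.** Section VIII.A gives about 18,600 adolescents, of whom 25% have completed the primary series: 0.25 × 18,600 = 4,650, as stated. At 1:1 this is 4,650 / 2 = 2,325 per arm. Neither reading of the control condition changes these numbers.

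**2. Timing of the delayed letter.** Section VII.A counts the endpoint over the 90 days after randomization. Section VI sends the control letter only after that period. The overlap between the delayed letter and the endpoint window is therefore zero days, and a booster prompted by that letter falls outside the outcome.

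**3. The passages side by side.**

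| Place | Control receives | Time limit |
|---|---|---|
| I, Synopsis | no notice | none given; endpoint is 90 days |
| VI, Intervention | study reminder by letter, to all | after 90 days |
| VI.A, Randomization | label: no reminder | none given |
| VIII.A, Sample Size | reminder intended for all eligible | none given |

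Section VI is the only place that says what is done and when. The label in Section VI.A stands under it and merely tells the two arms apart. Section VIII.A agrees with it. Only the synopsis sentence, a summary, lacks the qualifier.

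**4. What the notice is.** The synopsis sentence follows one that defines the notice as a single reminder for adolescents due for a booster. Read in that order, the control sentence refers to this notice. It also calls the arm usual care, which ordinarily means that routine practice goes on.

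**5. Routine letters.** COVID-19 vaccine was added to them in summer 2021. The Background dates the adolescent booster recommendations to December 2021 (ages 16-17) and January 2022 (ages 12-15), so the change came before any booster advice for this age group. The letters are not said to mention the booster, and trial participants have already finished the primary series. No section suspends the letters in either arm.

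**6. Can a size be put on it?** Only by assumption. If routine letters go to both arms alike, the risk difference shrinks by

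share aged 12 × share of them sent a routine letter × overlap,

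where overlap is 0 if the letter effects add and 1 if the study reminder adds nothing after a routine letter. With ages spread evenly over six years (assumed), the share aged 12 is 1/6 = 16.7%.

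- Overlap 0: no shrinkage.
- A quarter sent letters, overlap one half (both assumed): 0.167 × 0.25 × 0.5 = 2.1%.
- All sent letters, overlap 1: 16.7%.

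None of these three inputs is in the protocol. The shrinkage is also measured against a control group that gets no routine letters, which is not the stated comparison of reminder against usual care. The figures therefore show no error in the plan.

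**The case for a change.** The strongest case for acting is that what the control arm receives, and when, is core protocol content that should not be left to a statistical analysis plan. The synopsis and Section VI do differ on their face, and the label in Section VI.A repeats the unqualified wording. Because the intervention uses the same centralized reminder system as the routine letters, it is reasonable to ask how the two were kept apart. The repair would take a few words and one factual sentence.

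Part of this stands. The synopsis sentence is incomplete, and a sentence on routine letters would help a reader. But incomplete is not wrong in effect: anyone carrying out the trial from Section VI does the right thing, and the endpoint window makes the delayed letter harmless. The reading in which routine letters are stopped for controls alone has no support in the text. It needs "any" to outweigh both the definition just before it and the name of the arm. The rest of the argument rests on what the Background leaves unsaid, not on anything the protocol states wrongly.

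**Conclusion.** No change to the plan is called for. The mismatch is a clerical slip in a summary sentence, completed by Section VI. Its effect on the primary comparison is nil, because the control letter falls wholly after the 90-day window.

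The silence on routine letters is a gap that analysts would fill sensibly by treating them as part of usual care in both arms. The trial then compares the study reminder plus usual care with usual care alone, and randomization protects that comparison. This rests on one assumption: that routine letters were handled alike in the two arms, which is what usual care implies and what nothing in the protocol contradicts. Any effect of the routine letters on the size of the difference cannot be derived from the document and may be zero.

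Adding the time limit to the synopsis would be harmless tidying. It would alter no design feature, sample figure, endpoint or analysis.

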## II. BACKGROUND

To increase protection against SARS-CoV-2 infection, a single COVID-19 booster dose was recommended in the United States for adolescents aged 16-17 years in December 2021 and 12-15 years in January 2022. Uptake of the first COVID-19 booster dose among children and adolescents has been suboptimal. As of August 2022, booster dose coverage among adolescents aged 12 through 17 years was 33% compared to 70% among adults aged  $\geq 65$  years.

Centralized reminder and recall systems have been shown to be a cost-effective strategy to increase vaccination rates. Reminder and recall at Marshfield Clinic Health System (MCHS) are centralized and target young children aged 18-23 months and adolescents aged 12 years. In accordance with CDC and MCHS vaccination recommendations, COVID-19 vaccine was added to the reminder/recall letters for 12-year olds due for tetanus, diphtheria, and acellular pertussis vaccine (Tdap), meningococcal conjugate vaccine (MenACWY), or human papillomavirus (HPV) vaccine in the summer of 2021.

Beginning January 2022, individuals aged 12 and older who have completed the primary series were eligible to receive COVID-19 boosters. We propose to assess the efficacy of a one-time reminder/recall targeting adolescents aged 12-17 years who are eligible, but have not yet received the booster vaccine.

[figure not shown]
The intervention will leverage the existing MCHS's centralized reminder/recall system and process for enrolling patients for text and email communication regarding appointments and healthcare updates. The proposed intervention is a component of a larger project funded by the Centers for Disease Control and Prevention (CDC) to understand and address determinants of rural-urban differences in vaccine uptake among adolescents in the upper Midwest (NCT05148559).

## A. Marshfield Clinic Health System

Marshfield Clinic Health System is a large integrated regional healthcare system that serves a predominantly rural population. MCHS has over 10,000 employees working at 55 clinical locations throughout central, western, and northern Wisconsin, serving over 18,600 adolescents aged 12-17 years. The MCHS primary service area encompasses 32 counties in Wisconsin, including 70% of the state's rural counties (**Figure 1**).

**Figure 1. Marshfield Clinic Health System Service Area and Rural/Urban Classification of Counties based on Urban Influence Codes**

[USDA ERS - Urban Influence Codes](#)

## III. STUDY OBJECTIVE

To assess the efficacy of a one-time reminder/recall for COVID-19 booster dose sent via the parent's preferred method of communication among adolescents aged 12-17 years.

## IV. STUDY POPULATION

The target population is parents of MCHS adolescent patients aged 12-17 years who are due for a COVID-19 booster dose. Booster eligible patients were those who completed the COVID-19 primary series, defined as receipt of 2 doses of Pfizer/BioNTech mRNA vaccine  $\geq 17$  days apart, and were due for the COVID-19 booster (i.e.,  $\geq 5$  months since their second dose). Inclusion and exclusion criteria are outlined below.

### A. Inclusion Criteria

- Marshfield Clinic Health System patient aged 12-17 years with at least one preventive visit or two evaluation & management visits with a MCHS provider in the last 36 months
- Due for at COVID-19 booster dose (completed the COVID-19 primary series and it has been  $\geq 5$  months after the second dose)

## **B. Exclusion Criteria**

- Primary care provider is not affiliated with MCHS
- Opted out of MCHS's centralized vaccine reminder notifications
- Received COVID-19 vaccine off label
- Missing or invalid contact information
- Deceased

## **V. INTERVENTION PERIOD**

The intervention will be conducted in Spring 2022, as soon as possible after IRB approval is obtained.

## **VI. INTERVENTION**

The intervention (reminder/recall) consisted of a one-time booster dose reminder sent to parents using their specified preferred communication method (postal mail, email, or text). The default preferred communication method will be postal mail (letter) if text or email is not specified in the electronic health record. The reminder/recall message will differ for those who will receive text versus letter or email, due to restrictions on privacy and length of text messages ([APPENDIX](#)). The usual care group will not receive the reminder/recall until after the 90-day evaluation period. All persons in the usual care group will receive the reminder/recall via mailed letter.

### **A. Randomization**

Eligible adolescents will be stratified based on communication method and rurality (using home address). Each patient who is eligible at the time of data extraction/randomization will be assigned a random number, which will be used to facilitate stratified random sampling. Within each strata, the random number will be used to assign patients to intervention (reminder/recall sent via postal mail, text or email) or usual care (no reminder/recall) arm in a 1:1 ratio.

## **VII. OUTCOME MEASURES**

### **A. Primary Endpoint**

The primary endpoint will be documentation of receipt of a COVID-19 booster dose during the 90 days after randomization (90-day evaluation period).

Receipt of COVID-19 booster dose will be obtained from data available from the MCHS electronic health data, which includes a local vaccination registry that exchanges vaccination data from the state immunization registry.

## **VIII. PLANNED ANALYSIS**

Data will be analyzed using the data analysis software, SAS. We will calculate the absolute difference in COVID-19 booster dose receipt between study groups, as well as confidence intervals. We will also assess differences between arms using Chi-square tests, Student's t-test and Wilcoxon rank sum test where appropriate.

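### The randomization is stratified by communication method and rurality, but the analysis named in the protocol does not use those strata, which makes it slightly conservative if uptake differs between them

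*Protocol*

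**What the plan says.** Protocol, section VI.A (Randomization), forms strata from the communication method (postal mail, text or email) and from rurality based on home address. It then states: "Within each strata, the random number will be used to assign patients to intervention" or to the "usual care (no reminder/recall) arm in a 1:1 ratio".

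Section VII.A defines one binary primary endpoint: "documentation of receipt of a COVID-19 booster dose during the 90 days after randomization".

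Section VIII (Planned Analysis) names the estimator: "We will calculate the absolute difference in COVID-19 booster dose receipt between study groups, as well as confidence intervals". It names the tests next: "We will also assess differences between arms using Chi-square tests, Student's t-test and Wilcoxon rank sum test where appropriate". No stratified or covariate-adjusted analysis is named anywhere in the protocol, and none is ruled out.

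Section VIII.A gives the expected size, "25% or about 4,650 have completed the COVID-19 primary series and may be due for the booster dose", and says that no power calculation was made.

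**The concern.** When each stratum is split equally, differences in uptake between channels, or between rural and urban homes, cannot contribute to the difference between arms. An overall interval and an overall Chi-square test still include that variation in their standard error. If the strata differ, the interval is wider and the test weaker than the design allows.

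This matters here for two reasons. The sample is whoever is eligible, so lost precision cannot be made up by enrolling more patients. The protocol's Background also places the trial in a project on rural-urban differences in adolescent vaccine uptake, so unequal uptake by rurality is a real possibility.

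A second, smaller point is that section VIII does not say whether an overall or a stratified version is primary. The choice between two intervals and two p-values stays open.

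**Working it through.** **Inputs from the protocol**
- Expected number eligible: 0.25 × 18,600 = 4,650, which reproduces the figure in section VIII.A.
- With 1:1 allocation, n = 4,650 / 2 = 2,325 per arm.
- Three communication methods. With rurality taken as two levels (an assumption), there are six strata.

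**Assumptions (not in the protocol)**
- Two-sided 5% level and a fixed 1:1 split in every stratum.
- Stratum shares w_k: rural letter .35, urban letter .25, rural text .12, urban text .10, rural email .10, urban email .08.
- Uptake p_k in the same order:
  - equal: .20 throughout
  - 5-point gaps: .163/.213/.213/.263/.188/.238
  - 10-point gaps: .126/.226/.226/.326/.176/.276
  - 15-point gaps: .089/.239/.239/.389/.164/.314
  - wide: .05/.20/.25/.40/.25/.40

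In the gap scenarios urban exceeds rural by the gap, text exceeds letter by the gap, and email lies halfway between them. Mean uptake is 20%, or 19.45% in the wide scenario.

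**Formulas**

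With a fixed split, both arms have the same stratum shares. The overall difference therefore equals the stratum-weighted difference Σ w_k(p̂_1k − p̂_0k). Under no effect:
- actual variance = (2/n) · V_s, with V_s = Σ w_k p_k(1 − p_k)
- variance used by the ordinary interval and test = (2/n) · V_o, with V_o = p̄(1 − p̄) = V_s + Σ w_k(p_k − p̄)²

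The last term is the between-stratum part, which is counted although the design has removed it.

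- Half-width = 1.96 · √(2V/n)
- Excess width = √(V_o/V_s) − 1
- Actual type I error of the ordinary test = 2[1 − Φ(1.96 · √(V_o/V_s))]

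**Worked case, 10-point gaps**
- V_o = .20 × .80 = .1600. V_s = .1557. Between-stratum part = .0043, or 2.67% of V_o.
- Ordinary half-width: 1.96 · √(2 × .1600/2325) = 2.30 points.
- Stratified half-width: 1.96 · √(2 × .1557/2325) = 2.27 points.

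| Scenario | Variance reduction | Half-width, ordinary / stratified (points) | Excess width | Type I error, ordinary test |
|---|---|---|---|---|
| Equal | 0% | 2.30 / 2.30 | 0% | 5.0% |
| 5-point gaps | 0.67% | 2.30 / 2.29 | 0.3% | 4.9% |
| 10-point gaps | 2.67% | 2.30 / 2.27 | 1.4% | 4.7% |
| 15-point gaps | 6.01% | 2.30 / 2.23 | 3.1% | 4.3% |
| Wide, 5% to 40% | 9.95% | 2.28 / 2.16 | 5.4% | 3.9% |

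**Power.** For an assumed 3-point effect, stratifying raises power from about 70% to 71% with 10-point gaps and from about 71% to 73% with 15-point gaps.

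**Sensitivity to the assumed shares and mean**
- With random stratum shares (20,000 draws, mean uptake 20%), 95% of draws gave an excess width of 0.4-2.2% with 10-point gaps and 0.9-5.1% with 15-point gaps.
- At a mean of 10% with the shares above, the excess is 0.6% with 5-point gaps and 2.5% with 10-point gaps.

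**Simulation check**
- With 40,000 trials per scenario, rejection under no effect (ordinary / Cochran-Mantel-Haenszel) was 4.9/4.9%, 4.7/4.8%, 4.7/5.0% and 4.2/5.0% for equal strata and 5-, 10- and 15-point gaps. The ordinary and Mantel-Haenszel differences agreed to within 1e-16.
- A second simulation used other shares (35/20/25/5/10/5%), lower uptake and 200,000 trials per setting. Type I error of the ordinary test was 4.9%, 4.6% and 3.8% with strata running 8-14%, 5-25% and 3-45%. The stratified test stayed at 4.9-5.0%, and neither estimate was biased.
- With an independent coin flip per patient in place of a fixed split, the ordinary test was nominal in the two settings run (4.9-5.0%).

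**The case against.** The strongest reply is that this belongs in the statistical analysis plan, which is not available here. Section VIII is a three-sentence outline. "Chi-square tests" could include the Cochran-Mantel-Haenszel test, and a t-test and a Wilcoxon test do not suit a binary endpoint, so the list looks like a general toolbox. That limits the point: the wording leaves room for a stratified analysis. It does not remove it, because the section does name an effect measure and tests, and as ordinarily read they ignore the strata.

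It can also be said that nothing is invalid. That is correct: the estimate is unbiased, the error is in the safe direction, and no stated power target is missed. The gain is small and rests on assumed stratum rates, which is also correct.

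Finally, the conservatism needs a fixed split within strata. Section VI.A speaks of stratified random sampling and 1:1 assignment within strata, which supports that reading, but it does not spell out the mechanism. Under coin-flip assignment the ordinary test would not be conservative.

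These replies limit how much the point matters. They do not show it to be wrong.

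**Conclusion.** The concern holds as a modest loss of efficiency, not an error that threatens the result. The trial is randomized within strata that the named analysis does not use.

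The ordinary interval is too wide by 0% to about 3% for gaps of up to 15 points, and by 5.4% in the widest scenario. Power rises by about 1 to 2 points in the 10- and 15-point scenarios. If uptake is equal across strata, nothing is lost.

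These sizes rest on assumed stratum shares, uptake, effect size and significance level, and on a fixed 1:1 split. The direction (no bias, type I error at or below 5%) does not depend on the assumed shares or rates. Because the repair is almost free and leaves the estimate as it is, it should be made.

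**What to change.** Add one sentence to section VIII: the primary estimate is the Mantel-Haenszel risk difference stratified by communication method and rurality, with the matching stratified 95% confidence interval, and the primary test is the Cochran-Mantel-Haenszel test over the same strata. It would help to confirm in section VI.A that each stratum is split in a fixed 1:1 ratio.

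The cost is a few lines of SAS on variables already in the randomization file. With exact 1:1 strata only the interval and p-value change.

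On timing, section V places the intervention in Spring 2022 and a reference was retrieved in September 2022, so the 90-day window may already have closed for this version. If outcomes had been seen when the sentence was added, the report should say so.

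If the statistical analysis plan already specifies a stratified primary analysis, section VIII need only be brought into line with it.

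### The named analysis is unadjusted and may forgo a small, nearly free gain in precision from age and time since becoming booster-due, both known for every patient

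*Protocol*

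**What the plan says.** The endpoint in section VII.A is binary: "documentation of receipt of a COVID-19 booster dose during the 90 days after randomization". For the comparison, section VIII (Planned Analysis) says "We will calculate the absolute difference in COVID-19 booster dose receipt between study groups, as well as confidence intervals", followed by "We will also assess differences between arms using Chi-square tests, Student's t-test and Wilcoxon rank sum test where appropriate". No covariate, stratum or model is named.

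The inclusion criteria in section IV.A cannot be applied without two baseline values. One is age: "Marshfield Clinic Health System patient aged 12-17 years with at least one preventive visit". The other is the second-dose date, because the patient must have "completed the COVID-19 primary series and it has been" at least 5 months.

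Section VI.A stratifies randomization by communication method and rurality, and within strata patients go to the reminder arm or the "usual care (no reminder/recall) arm in a 1:1 ratio". Age and vaccination timing are not strata.

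Section VIII.A takes all eligible patients, estimates about 4,650, and says "Therefore, power calculations were not done". Section II dates the booster recommendation to "adolescents aged 16-17 years in December 2021 and 12-15 years in January 2022".

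**The concern.** Every patient enrolled is still unboosted at randomization. Some have only just become due, while others have been due for months without taking the dose. It is plausible that these patients differ in 90-day uptake, and that uptake also varies with age. If so, part of the outcome variance can be predicted from data already in the eligibility extract, and an unadjusted comparison counts that part as noise.

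The size cannot be raised, because the whole eligible population is already used. An efficient analysis is then one of the few ways left to narrow the confidence interval. Only precision is at stake; the validity of the result is not.

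**Working it through.** **Inputs from the protocol.** 18,600 adolescents and 25% with a completed primary series (section VIII.A); 1:1 allocation (section VI.A); a binary 90-day endpoint (section VII.A).

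**Inputs assumed, because the protocol gives none.** Two-sided 5% level, no dropout, and 90-day control uptake of 5%, 10% or 20%. Age is spread evenly over 12 to 17 years and vaccination timing evenly over 5 to 12 months since the second dose. The two are independent, uptake rises with age and falls with elapsed time, and each has an odds ratio of 1.2, 1.5 or 2.0 per standard deviation.

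**Step 1, the plan's own figure.** 18,600 × 0.25 = 4,650, which reproduces. That is 2,325 per arm. It is a ceiling, since section VIII.A says only that these patients might be due. There is no power figure to reproduce.

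**Step 2, raw precision.** SE = √(2p(1−p)/2,325). At p = 0.10 this is √(0.18/2,325) = 0.880 percentage points, so the 95% half-width is 1.96 × 0.880 = 1.72 points. At 5% and 20% uptake the half-widths are 1.25 and 2.30 points.

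**Step 3, effect of adjustment.** Let R² be the share of outcome variance explained: the variance of the predicted probabilities divided by p(1−p). Then adjusted SE = raw SE × √(1−R²), and effective N = 4,650/(1−R²).

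| Control uptake | Odds ratio per SD | R² | SE ratio | Gain in effective N |
|---|---|---|---|---|
| 5% | 1.2 | 0.003 | 0.998 | 0.3% |
| 5% | 1.5 | 0.016 | 0.992 | 1.6% |
| 5% | 2.0 | 0.046 | 0.977 | 4.8% |
| 10% | 1.2 | 0.006 | 0.997 | 0.6% |
| 10% | 1.5 | 0.029 | 0.985 | 3.0% |
| 10% | 2.0 | 0.081 | 0.959 | 8.8% |
| 20% | 1.2 | 0.011 | 0.995 | 1.1% |
| 20% | 1.5 | 0.049 | 0.975 | 5.2% |
| 20% | 2.0 | 0.128 | 0.934 | 14.7% |

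In the middle case (10% uptake, odds ratio 1.5) the half-width goes from 1.72 to 1.72 × 0.985 = 1.69 to 1.70 points. Effective N goes from 4,650 to 4,650/0.971 ≈ 4,789.

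**Step 4, simulation.** In 1,500 simulated trials of 4,650 patients at 10% uptake, linear adjustment was compared with the raw difference. The ratios of the standard deviations of the two estimates were 0.995, 0.986 and 0.961, against formula values of 0.997, 0.985 and 0.959.

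**Step 5, power.** At 10% control uptake, a difference of 2.60 points has 80% power unadjusted. With R² of 0.01, 0.05, 0.10 and 0.15, power becomes 80.4%, 82.0%, 84.0% and 86.0%.

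**Step 6, which timing variable.** A patient becomes due at the later of two dates: second dose plus 5 months, and the recommendation date for the patient's age group. For ages 12–15 the latter is January 2022 (section II). Any 12–15-year-old with a second dose before about August 2021 therefore became due at the same time, whatever the exact dose date. Within that group, time since the second dose says nothing about how long the booster has been passed up. Time since becoming due is the better covariate, and it can be derived from the same extract. The table models elapsed time since the second dose, so it shows a range of prognostic strengths and is not a forecast for this variable.

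**The case against.** The strongest objection is that nothing here is wrong. In a 1:1 randomized trial the raw risk difference is unbiased and the Chi-square test is valid. Covariate adjustment is often left to a statistical analysis plan, and none is shown. Section VIII does not call its methods primary or unadjusted, and its list of tests ends with a qualifier, so an adjusted absolute difference could be added later without contradicting it. All of this stands, and it is why the point is only an optional improvement. What remains is that the methods actually named are two-arm comparisons without covariates.

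A reader might infer that the trial definitely loses precision. The documents do not support that. They give no control uptake and no association of age or timing with uptake. For age, they show only that the recommendation dates were a month apart, which does not establish a difference in uptake among those still unboosted.

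A reader might also assume that most patients had been due for more than 3 months, which would help to make timing a strong predictor. The dates make that doubtful. The intervention is set for Spring 2022 (section V), and the release cited for the extension to ages 12–15 is dated January 5, 2022 (section X). Before early April no 12–15-year-old could have been due that long.

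Finally, the gain is small in absolute terms, a few hundredths of a percentage point of half-width in the middle case, and the protocol sets no power target that could be missed.

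**Conclusion.** The point holds as a possible free improvement. The protocol names an unadjusted comparison, two potentially prognostic baseline values are complete for every patient, and the size is fixed. Across the assumed gradients the gain is about 0.3% to 15% in effective sample size, around 3% in the middle case, with a standard error under 1% to about 7% smaller.

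The size of the gain rests wholly on the assumed control uptake and odds ratios. If the covariates predict little, almost nothing is gained, and at this sample size almost nothing is lost. If fewer than 4,650 patients are eligible, the interval is wider but the relative gain is the same. The stronger reading, that the planned analysis is biased or invalid, is not supported.

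**What to change.** In section VIII, prespecify the main estimate as a covariate-adjusted risk difference with its confidence interval. It can come from a logistic model standardised to the risk difference or from a linear model with robust standard errors. Include:

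- arm;
- the randomization strata, communication method and rurality;
- age group (12–15, 16–17);
- time since becoming booster-due, derived from the second-dose date and the age-specific recommendation date in section II.

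Fix the form of each covariate before outcome data are seen. Keep the raw difference and Chi-square test as supportive. Prespecifying also removes any later choice between raw and adjusted results.

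The cost is a sentence or two in the protocol and a few lines of SAS. No new data, patients or procedures are needed, and the estimand remains the absolute difference in 90-day booster receipt.
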